3.6 Interviews, Focus Groups, Surveys, and/or Observations

A. Administration

- *Timing and Frequency*

Pre-interview/baseline assessment, intervention, and post assessment follow up post-intervention (within a week).

- *Location*

Telephone-based delivery of the intervention and in person or over the phone assessments. Cancer patients may opt to have their interview(s) during infusion at participating sites (FHCC, UT Southwestern/PHHS, Confluence Health).

***Additional measures to protect participants in the in-person interviews or usability testing from COVID-19 related exposure and infection.** In-person interviews will only be conducted in line with all the safety regulations and recommended procedures for vulnerable and at-risk patient populations. As such, no in person approaches will happen prior to the appropriate approval and authorization at each participating site. In the even in person approaches are approved, study personnel will ensure proper PPE is worn by approaching study staff, proper social distancing is observed, and that all patients consent to and are comfortable with in person interviews. Due to potential risks, telephone-based interviews will be promoted among participating patients, when available.

- *Person Identifiers*

Clinical variables will be collected from medical records and will include the following: cancer diagnosis and stage, treatment received, co-morbid conditions (i.e., Charlson Comorbidity Index, CCI), and Karnofsky performance status.

B. Study Instruments

Feasibility will be measured by intervention completion (Benchmark: $\geq 70\%$ complete the intervention sessions). Acceptability will be measured by a single-item question assessing helpfulness of the intervention (1 = not at all helpful, 5 = very helpful) as well an open-ended question about helpfulness of the intervention (“What was helpful about the intervention?”) (Benchmark: $\geq 70\%$ rate it as “helpful” or “very helpful”). Demographics will be measured via self-report assessing: age, gender, race, ethnicity, marital status, employment status, education, income, religion, insurance coverage, national origins (e.g., Mexican), cultural heritage, and acculturation.⁴² Clinical variables will be assessed using records from medical charts and will include the following: cancer diagnosis, treatment, site, and stage; co-morbid conditions, and Karnofsky⁴³ performance status.

Quality of life will be measured using the validated, 27-item Functional Assessment of Cancer Therapy-General (FACT-G) scale.⁴⁴ Cultural beliefs will be measured using three brief scales developed for the present studies (included in the R01).

Fatalismo⁴⁵ will be measured using a 4-item scale assessing the acceptance of belief that all events are predetermined and inevitable. Personalismo^{46,47} will be measured using a 4-item scale assessing the existence of a warm, personal relationship with the medical professional and trust based on mutual respect. Respeto⁴⁸ will be measured using a 4-item scale assessing the degree to which patients endorse the role of authority in following doctor’s orders. Familial beliefs will be measured using two brief scales developed for the present studies (included in R01). Familismo^{61,62}

will be measured using a 5-item scale assessing the degree of family loyalty and cohesion. Related to *familismo*, *filial duty*⁴⁹ will be measured with a 6-item scale assessing the degree to which children should be involved in caring for their elderly parents. Religious/spiritual beliefs will be measured with two scales: (1) *Religious coping* will be measured using *Pargament's brief RCOPE*,⁵⁰ which is a validated 14-item scale ($\alpha > .80$ ⁵⁰) assessing the extent to which patients engage in 7 types of positive and 7 types of negative religious coping. (2) *Religious beliefs about EOL medical care* will be measured using a 9-item scale. We have recently begun to validate this scale among advanced cancer patients in our prior studies.⁵¹ Potential confounders to be measured include *terminal illness acceptance*, which will be assessed using our validated, single-item question,^{19,52} which asks patients how they would define their current health status and *illness understanding*, a single item measure that assesses understanding of incurability of illness. We will use the Advance Care Planning Engagement Survey, which is a validated 49-item scale ($\alpha=.94$)¹ designed to assess knowledge, readiness/motivation, and self-efficacy of ACP. Engagement in ACP will measure two key elements of ACP. First, *EOL care discussions* will be measured by asking patients to self-report whether they have discussed any of the following: (1) wishes they have about the care they would like to receive if they were dying and/or (2) advance care directives, with an oncology provider or family member: DNR orders, living wills, durable powers of attorney for health care, assignments of health care proxies (yes/no format). Second, *completion of advance directives* will be assessed by examining the medical chart for completed advance directive documents (DNR order, living will, durable power of attorney, health care proxy). Patient's Medical Status. Patients' current and past cancer diagnoses, the dates of each, patients' Karnofsky performance score⁴³ and the number and type of oncology providers seen at that clinic will be obtained from the patient's medical chart. Advance Directives and Referrals for Palliative Care. Patient's medical charts will be reviewed for documentation of advance directives and referrals for palliative care during the study observation period (consent to interview).

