Study Duration:	November 1, 2021 to April 30, 2024
Participant Duration:	4 to 6 weeks

Primary Objective:	To determine the feasibility, acceptability, and potential efficacy of the culturally competent communication to improve engagement in ACP (i.e., end-of-life discussions with providers and families, completion of advance directives) for Latino patients with advanced cancer.
Secondary Objectives:	Not applicable
Exploratory Objectives:	Not applicable
Endpoints:	
Feasibility will be measured by intervention completion (Benchmark: $\geq 70\%$ complete the intervention sessions).
 
Acceptability will be measured by a single-item question assessing helpfulness of the intervention (1 = not at all helpful, 5 = very helpful) as well an open-ended question about helpfulness of the intervention ("What was helpful about the intervention?") (Benchmark: $\geq 70\%$ rate it as "helpful" or "very helpful").
 
Advance Care Planning Readiness will be measured using the Advance Care Planning Engagement Survey, which is a validated 49-item scale ($\alpha=.94$)¹ designed to assess knowledge, readiness/motivation, and self-efficacy of ACP. Engagement in ACP will measure two key elements of ACP. First, EOL care discussions will be measured by asking patients to self-report whether they have discussed any of the following: (1) wishes they have about the care they would like to receive if they were dying and/or (2) advance care directives, with an oncology provider or family member: DNR orders, living wills, durable powers of attorney for health care, assignments of health care proxies (yes/no format). Second, completion of advance directives will be assessed by examining the medical chart for completed advance directive documents (DNR order, living will, durable power of attorney, health care proxy).

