3.5 Strategies for Recruitment and Retention

To recruit patients at FHCC, trained bi-lingual, bi-cultural research staff will review the electronic health record to identify potentially eligible patients. And will contact the treating oncologist to confirm initial eligibility and obtain permission to approach these patients about the study. Using the eligibility criteria outlined, study staff will screen participating oncologists' clinic schedules for patients that meet the inclusion criteria (e.g., cancer diagnosis and treatment status). Alternatively, oncologists will refer their patients directly to the study.

To recruit patients at Confluence Health, a clinical roster will be reviewed daily by oncologists or clinical team members. Potentially eligible patients will be identified and forwarded in a list to FHCC study staff. Trained bi-lingual, bi-cultural FHCC research staff will approach, determine eligibility, and consent eligible patients.

To recruit PHHS patients by UTSW study staff, the site PI ([name]) or trained bi-lingual, bi-cultural staff at UTSW will obtain verbal consent either in-person or over the phone from Parkland patients eligible for the study. All consented patients will then be given assessments/surveys. For patients randomized to the intervention condition, they will receive the telephone-based intervention by the FHCC study staff. These approaches are outlined and will be approved by the participating site's local IRB.

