3.7 Intervention (PLAN)

The intervention for this study, Planning For Your Advance Care Needs (PLAN), is a coaching-based communication information designed to be culturally competent. In PLAN, all coaching sessions will occur over the phone and be a maximum of 45 minutes to reduce patient burden. These sessions will focus on creating individualized messages and skill-building exercises based on patients' learning needs, goals, and values (as indicated on the intake form). The intervention will be delivered across three sessions, with the following modules, as based on prior communication competence coaching interventions:⁵³ (1) *Assessment* of current knowledge, motivation, and self-efficacy (action) as well as cultural and religious preferences/values surrounding EOL care (tablet-based intake questionnaire); (2) *clarification and correction of misconceptions* about EOL care and ACP; (3) *teaching* of relevant concepts (education about ACP and EOL care options); (4) *planning* (identifying goals of care, creating achievable goals of care, and creating strategies to communicate goals of care to providers and family members); (5) *rehearsal* of communication skills using role play exercises (practice question-asking, etc.); (6) *portrayal* of learned skills (patient applies learned skills in their oncology visit and/or with family members).

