3.9 Intervention Administration

A total of 50 Latino advanced cancer patients will be enrolled in this study and randomly assigned to the intervention (n=25) or control (n=25) condition. Pre-intervention, patients'

communication goals will be assessed. Then, patient will participate in the intervention or a usual care control condition. After participating in the intervention or control condition, patients' engagement in ACP will be assessed to determine if the intervention improved ACP engagement and planning.

The intervention itself will be administered by a fully trained, licensed social worker via telephone. This interventionist will use a culturally competent communication intervention to "coach" patients in how to be motivated for and to actually engage in ACP, and will be bilingual in Spanish and English.

Patients randomized into the control group will receive usual care. For usual care, patients will engage in standard care with no modifications. Thus, ACP discussions will only occur as they do in usual clinical care (i.e. brought up in clinical encounters).

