as well as satisfaction and helpfulness ratings to determine feasibility and acceptability based on those values being equal to or greater than 70%. We will also conduct qualitative analyses on the open-ended questions related to helpfulness. Thematic analysis using an iterative process will be conducted for all qualitative analyses.⁵⁵⁻⁵⁹ A coding scheme and codebook will be created to analyze transcripts of the responses to the open-ended question. Transcripts will be coded separately by two individual coders for manifest (e.g., frequencies) and latent (e.g., underlying themes) variables. If discrepancies occur, a third coder will resolve these conflicts. Interviews will continue until thematic saturation is achieved.^{60,61} Based on our prior field testing of interventions with patients with advanced illness, we anticipate reaching saturation with n=10 participants. Thus, n=25 in the experimental condition should be well powered to reach thematic saturation.

To examine potential efficacy, preliminary analyses will utilize t-tests to compare the two groups on baseline characteristics (e.g., education, age). Using a criterion of $p < .10$, any variables that are different among the groups will be included in the final logistic regression models as potential confounders. To test the study aim, five separate logistic regression models will be run in which ACP outcomes (yes/no to EOL discussions with family and providers; and the completion of advance directives DNR, health care proxy, and living will) will be predicted by the group variable (CCC intervention vs. control). The statistical power of the proposed logistic regressions to detect a minimum odds ratio of 2.0 for dichotomous outcome measures of ACP, for a two-tailed test with power $(1 - \beta)$ equal to 0.80, and $\alpha = 0.05$, requires a sample size of 113. Our proposed sample size of n=50 will be underpowered if the effect size is small but adequately powered if it is large. However, this study is a preliminary pilot and the main focus and goal of this is to determine feasibility, acceptability, and to provide preliminary data to inform a fully-powered RCT in future research (R01 submission).

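### The end-of-life discussion item leaves oncology provider undefined and does not exclude the PLAN coach, so some PLAN patients could count coaching calls as a provider discussion

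*Combined protocol and SAP*

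**What the plan says.** Section 3.6 (Study Instruments) measures discussions by "asking patients to self-report whether they have discussed any of the following: (1) wishes they have about the care they would like to receive", and the sentence continues "if they were dying and/or (2) advance care directives, with an oncology provider or family member: DNR orders, living wills". The Endpoints row of the Protocol Summary has the same wording. Section 7 analyses the answers as "yes/no to EOL discussions with family and providers", which makes two of the five logistic models. The other three concern DNR order, health care proxy and living will, and section 3.6 takes directive completion from the medical chart.

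On the coach, section 3.9 states: "The intervention itself will be administered by a fully trained, licensed social worker via telephone". Section 3.5 says of Parkland patients randomized to PLAN that "they will receive the telephone-based intervention by the FHCC study staff". The session content in section 3.7 includes "cultural and religious preferences/values surrounding EOL care (tablet-based intake questionnaire"), education on care options, setting goals of care, and "creating strategies to communicate goals of care to providers and family members", followed by role play. Section 3.8 gives three sessions about a week apart and places the post-intervention assessment within a week of the last one. Controls receive usual care with no coaching (section 3.9).

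**The concern.** The outcome is meant to capture a behaviour that coaching should produce: the patient talking to clinicians or family. The coaching itself is a conversation about the same subjects, held with a licensed professional from a cancer center. If the item does not clearly rule that conversation out, part of the measured outcome may be receipt of the intervention.

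Such an error would arise mainly in one arm and would push the comparison towards PLAN. Randomization and baseline covariates cannot remove it, because the intervention creates it. A bare yes/no answer with no record of the partner cannot be corrected afterwards. Section 7 says that the data are to inform a fully powered trial, so an inflated odds ratio could carry over into its planning.

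**Working it through.** **Step 1. What the item settles and what it leaves open.**

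- It names eligible partners: "with an oncology provider or family member: DNR orders, living wills, durable powers of attorney for health care".
- Neither section 3.6 nor section 7 defines oncology provider.
- The partner phrase follows item (2), directives. Item (1), wishes about care when dying, can be read with no partner attached.
- No section tells patients or interviewers to leave out PLAN sessions. Interviewer training (section 3.8) does not mention it.
- For UT Southwestern patients, section 3.5 has the lead center's coordinator and social worker carry out all remaining procedures by telephone. It does not say that the social worker stays out of the outcome interview.

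**Step 2. Which of the five models are exposed.**

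| Model | Source | Exposure to the coach being counted |
|---|---|---|
| Discussion with provider | self-report | exposed |
| Discussion with family | self-report | largely spared; the coach is not family |
| DNR, proxy, living will | chart | none |

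**Step 3. Illustration of size.** The documents give no misattribution rate, so there is no plan figure to reproduce for it. Inputs:

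- p0 = 0.32, the rate of end-of-life discussions among Latinos in section 2. This is a background rate, not a planning rate, and it is not split by partner.
- n = 25 per arm (section 7).
- f = the share of PLAN patients with no eligible discussion who answer yes because they count the coach. This is an assumption, shown as a range.
- No true effect of PLAN.

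Formulas: observed PLAN rate = p0 + (1 − p0) × f. Apparent OR = odds(observed PLAN rate) ÷ odds(p0), with odds(0.32) = 0.32/0.68 = 0.4706.

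Example at f = 0.30: 0.32 + 0.68 × 0.30 = 0.524; odds = 0.524/0.476 = 1.101; OR = 1.101/0.4706 = 2.34.

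| f | PLAN rate | Apparent OR | P(significant), chi-square | P(significant), Fisher |
|---|---|---|---|---|
| 0 | 32.0% | 1.00 | 5.4% | 2.4% |
| 10% | 38.8% | 1.35 | 8.8% | 4.6% |
| 20% | 45.6% | 1.78 | 18.6% | 11.5% |
| 25% | 49.0% | 2.04 | not run | not run |
| 30% | 52.4% | 2.34 | 34.5% | 24.3% |

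The last two columns come from exact binomial enumeration at 25 versus 25, two-sided at 0.05, without covariates. In patients: 0.68 × 25 = 17 would-be 'no' answers in PLAN, so f = 10% to 30% means 1.7 to 5.1 people.

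**Step 4. Sensitivity to the control rate.** With p0 = 20%, f = 10%, 20% and 30% give ORs of 1.56, 2.25 and 3.14. With p0 = 50% they give 1.22, 1.50 and 1.86.

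**Step 5. The plan's odds ratio of 2.0.** It serves here only as a yardstick. The sample size of 113 that section 7 attaches to it does not reproduce for a 1:1 group variable: the two-proportion formula at 32% versus 48.5% needs 276 in total. That is a separate matter, and nothing above depends on it.

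**The case against.** A reader might infer that the coaching sessions by themselves satisfy the endpoint. The documents do not support that. The item names an oncology provider or family member, so a patient who spoke only to the coach meets it only if the social worker is taken for a provider or item (1) is read without the partner phrase. Section 3.7 treats the coach as someone who prepares the patient to speak to providers and family. Section 3.4 describes the target conversations as those with loved ones and providers. Section 3.6 takes the oncology providers seen at the clinic from the chart, and section 3.5 calls the coach the study interventionist. For UT Southwestern and Confluence patients the coach phones from another institution, which makes confusion less likely there. This shows what the authors intended, and it stands. It is not an instruction within the measure.

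A reader might also infer that false positives can occur only in PLAN and that controls cannot meet the endpoint. Neither follows. Controls can have real discussions in usual care or at home. They also sit through research interviews on end-of-life beliefs and ACP (sections 3.6 and 3.8, Table 1), which a patient could conceivably miscount. The imbalance comes from the three coaching calls, so the error is mainly, not exclusively, in PLAN.

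The questionnaire and interviewer prompts are not in the documents and may already contain the exclusion. Section 7.2 relies on interviewers to clarify terms. That is a fair reason for caution about size. Finally, section 7 makes feasibility and acceptability the main aim, so no go/no-go decision hangs on this odds ratio.

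**Conclusion.** The gap is real but limited. The item names its discussion partners, leaves oncology provider undefined, ties the partner phrase clearly to only one of its two parts, and does not exclude PLAN sessions. Any resulting miscounting would mainly raise the PLAN arm's rate in the provider-discussion model. It would be wrong to read it as a bias in all five models.

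The size is unknown. The range of 1.35 to 2.34 for the apparent odds ratio assumes a 32% true rate in both arms, no effect, and misattribution of 10% to 30%, a fraction with no source in the documents. A reader might infer from the 25% row that an ineffective intervention would show the plan's odds ratio of 2.0. It would do so only if about a quarter of would-be 'no' answers were misattributed at that control rate, and nothing in the documents says that this happens. Because the correction is cheap and the error cannot be undone after data collection, the wording should be tightened.

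**What to change.** In section 3.6, in the matching Protocol Summary text, and in section 7:

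- Attach the partner restriction to both item (1) and item (2).
- Define oncology provider as a member of the patient's treating clinical team.
- Add to the item, in English and Spanish, in both arms and at both time points: *Do not count conversations with the PLAN coach or with research interviewers as part of this study.*
- When the answer is yes, have the interviewer record who the discussion was with.
- State the scoring rule: PLAN sessions and research interviews score 'no'. Real clinical discussions with a treating clinician who is also a study investigator still count. A blanket exclusion of study personnel would wrongly recode these; section 3.1 describes a site collaborator who directs palliative medicine programs at Parkland.

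The cost is a wording amendment for IRB review and a short translation. No extra patients, visits or staff are needed.

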1.1.2 Hypotheses / Research Questions

The culturally competent communication intervention will be feasible, acceptable, and result in greater engagement in ACP than those in the control condition.

2. Background and Significance

Latino/non-Latino, white disparities are prevalent in ACP and quality of EOL care. Cancer is the leading cause of death among US Latinos.² This highlights the importance of addressing advance care planning (ACP) for Latino cancer patients. So do recent U.S. Census Bureau statistics indicating that Latinos are the fastest growing minority group in the U.S., with expected growth rates of 57% from 2015 to 2050 (totaling to 103 million).³ Latino/white disparities are prevalent in end-of-life care planning and outcomes. For instance, terminally ill Latinos are less likely than non-Latino, whites (hereafter referred to as “whites”) to engage in ACP.⁴⁻⁸ ACP enables patients to achieve their preferred EOL goals of care. Latinos are significantly less likely than whites to engage in two main forms of ACP: (1) end-of-life discussions (32% vs. 85%)⁴ and (2) completing advance directives such as having a living will (9% vs. 67%) or naming a health care proxy (4% vs. 59%).⁴ Engaging in ACP is critical to receiving preferred end-of-life care. Among all groups, patients who engage in ACP have been shown to be significantly more likely to receive care in line with their end-of-life care wishes (86% vs. 30%)⁹ and to die in their preferred place (85% preferred home).¹⁰ The absence of ACP, in turn, is linked to higher rates of death in the Intensive Care Unit (ICU). ICU death is linked to greater physical and emotional distress and poorer quality of life.^{11,12} Latino patients are more likely than their white counterparts to receive aggressive care (e.g., CPR, ICU stays) at the end of life.¹³⁻¹⁵ They are also less likely to use hospice services.^{14,16-18} The aggressive care that Latinos often receive is generally contrary to their preferences and values,¹⁹⁻²⁴ associated with poorer quality of life,^{12,19,25,26} and very costly.¹³

[figure not shown]

Figure 1. Conceptual model of the role of communication competence and social psychological influences on engagement in ACP among Latinos.

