3.4 Exclusion Criteria

Patient exclusion criteria: (1) not fluent in English or Spanish; (2) severely cognitively impaired (as measured by Short Portable Mental Status Questionnaire scores of ≥ 6 to be delivered by trained study research staff during screening);⁴¹ (3) too ill or weak to complete the interviews (as judged by interviewer); (4) currently receiving hospice at the time of enrollment (to allow prediction of ACP); (5) children and young adults under age 18; and (6) patients deemed inappropriate for the study by their treating oncologist. Because the primary outcomes include both completion of advance care planning documentation as well as conversations around ACP, we have chosen not to add exclusion criteria around completion of advance directives. The goal of PLAN is two-fold – which is to increase completion of these documents but also to increase engagement in conversations around ACP with loved ones and providers (which can be present or not present despite completion of documents).

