Conduct of Patient Assessments. Patients' assessments will be conducted either in person in clinic or at home, or over the telephone depending on the wishes of the patient. Interviews will be conducted in English or Spanish depending on the preference of the patient. We have previously validated all measures to be used in samples of English- and Spanish-speaking advanced cancer patients, and all assessments will be translated into Spanish through Datagain, a professional translation service which utilizes HIPAA compliant procedures and has been used in prior studies by the PI. We will document the language in which the interview was conducted. Each interview will be conducted alone with the patient to permit greater freedom of expression and will be approximately 45 minutes in length. If patients appear depleted or otherwise unable to be interviewed at that time, the interviewer will reschedule the interview at a time and place of their choosing within a few days. Considerable care has been taken to ensure that the interviews are as brief as possible. All Spanish translated materials will be submitted for IRB approval after receiving approval for the English documents.

Medical Chart Extraction. Study staff will review participating patients' medical charts during the course of the study to extract information about patients' health and disease status, healthcare, documentation of advance care directives, and referrals for palliative care during the study observation period.

Reducing Missing Data. To reduce missing data, following all assessments study staff will review the contents and scan for missing information. If missing information is found, the staff member will contact the subject or review the medical chart to fill-in missing data.

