5.1 Schedule of Assessments

Table 1. Schedule of trial events

	Baseline	Post-intervention (with 1 week of completing intervention)	3 mos. after completion of intervention	Off Study
Informed consent	X			
Demographics	X			
Clinical variables				X
Acceptability		X		
Usability		X		
Feasibility		X		
Quality of life	X	X		
Cultural beliefs (Fatalismo, personalismo, respeto)	X	X		
Familial beliefs (Familismo, filial duty)	X	X		
Religious/spiritual beliefs (Religious coping, religious beliefs about end-of-life medical care)	X	X		
Terminal illness acceptance	X	X		
Illness understanding	X	X		
Readiness for ACP	X	X		
Engagement in ACP	X	X		
Healthcare utilization	X	X	X	
Goal-concordant care	X	X	X	

6. Data Reporting / Regulatory Considerations

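### No rule says how an advance directive completed before consent is coded; counting it as a success, as the undated endpoint definition implies, dilutes the odds ratio in three of the five efficacy models

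*Combined protocol and SAP*

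**What the plan says.** The Endpoints row of the Protocol Summary says completion of advance directives "will be assessed by examining the medical chart for completed advance directive documents". Section 3.6 repeats this and lists the documents: it "will be assessed by examining the medical chart for completed advance directive documents (DNR order, living will, durable power of attorney, health care proxy"). Neither sentence carries a date.

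At the end of Section 3.6 a separate chart-review sentence says records are "reviewed for documentation of advance directives and referrals for palliative care during the study observation period (consent to interview"). It does not say which interview; I take it to be the post-intervention one. Section 3.8, under medical chart extraction, again refers to "documentation of advance care directives, and referrals for palliative care during the study observation period".

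On eligibility, Section 3.4 states that "we have chosen not to add exclusion criteria around completion of advance directives", so patients with existing documents enter the trial knowingly.

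In Section 7, "five separate logistic regression models will be run in which ACP outcomes" are predicted by group; three of them concern directives (DNR, health care proxy, living will). Baseline variables enter only if the arms differ at p < .10. Table 1 in Section 5.1 schedules "Engagement in ACP" at baseline and post-intervention, but no text says how the baseline value is to be used.

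**The concern.** Take a patient who signed a living will a year before consent. By the endpoint definition this patient is a success; by the chart-review sentence the document falls outside the window. The plan gives the abstractor no rule.

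The two codings are not equally harmful. If prior documents count, both arms receive the same ready-made successes, which PLAN cannot have caused, and the odds ratio moves toward 1. If they do not count, these patients stay in both denominators as failures, which costs little. So the undated definition, followed as written, is the one that hides an effect. Section 7 says the pilot's data are meant to inform a fully powered trial, so a diluted odds ratio would carry forward into that design.

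**Working it through.** The plan states no figure for this point, so there is none to reproduce.

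**Inputs**
- Prior prevalence *b*: Section 2 cites 9% (living will) and 4% (health care proxy) for Latinos. These are background rates, not rates in the enrolled patients, and no DNR rate is given. I add 20% and 40% as assumptions to show the range.
- New completion in controls without the document, *c*: not stated. Assumed 5%, then varied.
- New completion with PLAN, *t*: from the odds ratio of 2.0 in Section 7, the only effect size named. Odds 2 × 0.05/0.95 = 0.1053, so *t* = 0.1053/1.1053 = 9.5%. A large effect, *t* = 35%, is assumed for comparison: (0.35/0.65)/(0.05/0.95) = 10.2.
- *b* is taken as equal in the two arms.

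**Formulas**
- Undated coding: success rates *b* + (1−*b*)*c* and *b* + (1−*b*)*t*.
- Window coding, prior documents coded as failures: (1−*b*)*c* and (1−*b*)*t*.

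**Example, *b* = 9%, odds ratio 2.0**
- Undated: 0.09 + 0.91 × 0.05 = 13.55% and 0.09 + 0.91 × 0.0952 = 17.67%; odds ratio 1.37.
- Window: 0.91 × 0.05 = 4.55% and 0.91 × 0.0952 = 8.67%; odds ratio 1.99.
- Ratio of the two: 1.45.

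| New completion, control vs PLAN | Prior | Undated OR | Window OR | Ratio |
|---|---|---|---|---|
| 5% vs 9.5% (OR 2.0) | 4% | 1.57 | 2.00 | 1.27 |
| | 9% | 1.37 | 1.99 | 1.45 |
| | 20% | 1.21 | 1.98 | 1.64 |
| | 40% | 1.12 | 1.96 | 1.76 |
| 5% vs 35% (OR 10.2) | 4% | 6.2 | 10.0 | 1.6 |
| | 9% | 4.4 | 9.8 | 2.2 |
| | 20% | 2.9 | 9.3 | 3.2 |
| | 40% | 2.1 | 8.6 | 4.1 |

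The window column stays close to the odds ratio among patients without the document (2.0 or 10.2); the undated column does not.

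**Sensitivity to *c***
- Commoner new completion shrinks the ratio. At 4% and 9% prior it is 1.15 and 1.28 for *c* = 10% with odds ratio 2.0, and 1.07 and 1.14 for 20% vs 35%.
- Rarer new completion enlarges it. With *c* = 2% and 9% prior it runs from 1.68 to 3.44 as the odds ratio for new completion goes from 2 to 8.
- If *t* = *c*, both codings give 1.

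**Unequal prior shares.** With 25 per arm, chance can move the undated result either way. With 4 prior documents under PLAN and 1 in control, and 5 vs 1 new completions, the undated coding gives 9/25 vs 2/25, odds ratio (9/16)/(2/23) = 6.47. The window coding gives 5/25 vs 1/25, odds ratio (5/20)/(1/24) = 6.0.

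**Does adjustment help?** Take 25 per arm, 5 prior in each, and new completion of 7/20 vs 1/20.
- Unadjusted, undated: 12/25 vs 6/25, odds ratio (12/13)/(6/19) = 2.92.
- Unadjusted, window: 7/25 vs 1/25, odds ratio (7/18)/(1/24) = 9.33.
- Logistic model with group and prior possession: group odds ratio 10.23 under either coding.
- Restricted to the 20 per arm without the document: (7/13)/(1/19) = 10.23.

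Adjustment therefore removes the coding dependence and matches the restricted analysis.

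**The case against.** The texts can be reconciled. The endpoint sentences name a source and a list of documents; the narrower chart-review sentence, echoed in Section 3.8, can be read as completing them, and the window coding then does little damage. Alternatively, the observation-period phrase may describe when staff look rather than when the document was made. That reading is weaker, because Section 3.8 gives the timing of review separately and then attaches the phrase to the documentation. This is an ambiguity rather than a flat contradiction, and baseline status is plausibly captured through Table 1. It is also a pilot whose stated focus is feasibility and acceptability. All of that stands, but it supplies neither a coding rule nor a required use of the baseline value.

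Three stronger inferences are tempting and unsupported:
- A reader might infer that the odds ratio changes two- to four-fold. That needs an assumed effect well above 2.0, with prior directives commoner than cited or new completion in controls very rare. At 2.0 with 5% control completion the ratio stays below 2 even at 40% prior. Recruitment through a palliative care clinic at UTSW (Section 3.5) makes a higher prior rate possible, but no rate is given.
- A reader might infer that adjustment fails because prior possession predicts the undated outcome perfectly. Only that covariate's coefficient diverges; the group estimate is sound, as shown above.
- A reader might infer that abstractors will code knowing the arm. The documents do not say whether they know it.

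**Conclusion.** The gap is real and should be closed before charts are abstracted. Patients with existing directives are eligible, the endpoint definition is undated, a later sentence implies a window, and no rule decides between them. The p < .10 screen does not guarantee the adjustment that would make the choice immaterial.

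Under the undated definition the effect is diluted in the DNR, proxy and living-will models; under the window it is attenuated only slightly (9.8 against 10.2 at 9% prior with the large effect). With 5% new completion in controls, the ratio between the two odds ratios at 4% and 9% prior is about 1.3 to 1.5 for an odds ratio of 2.0, and about 1.6 to 2.2 for 5% versus 35%. For those effects it is larger only if prior directives are commoner. These sizes rest on assumed completion rates, on background prevalences standing in for the enrolled patients, and on equal prior shares by arm.

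**What to change.** Reconcile the Protocol Summary, Section 3.6 and Section 3.8 around one rule, and name the interview that closes the window.

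Record the date of each directive and whether each document was in the chart at baseline, using the baseline assessment of ACP engagement already in Table 1. For each directive model, define the outcome as that document newly completed after randomization, and analyse the patients without it at baseline. Because that status precedes randomization, the randomized comparison is kept. Equivalently, always adjust for baseline possession of that document, whatever the p-value of the baseline comparison. The restricted form is easier to report, since the possession coefficient has no finite estimate. Report the number with each prior document by arm.

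The cost is a date field, a baseline field per document and a few sentences. Patients with a prior document add no information to that document's model: 0.04 × 50 = 2 at 4% prior, 0.09 × 50 = 4.5 at 9%, and 0.40 × 50 = 20 at 40%. If prior directives prove common, the loss of precision is substantial and should be stated alongside the estimate.
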